#### 6.4.3.2 AEs and SAEs

AEs will be summarized using MedDRA System Organ Class and preferred terms. Tables will show by treatment arm the number and percentage of participants experiencing an AE within a System Organ Class or within preferred term category by severity or by relationship to study product. For the calculations in these tables, a participant with multiple AEs within a category will be counted once under the maximum severity or the strongest recorded causal relationship to study product. Formal statistical testing comparing arms is not planned since interpretation of differences must rely heavily upon clinical judgment.

A listing of SAEs reported to the DAIDS Regulatory Support Center (RSC) Safety Office will provide details of the events including severity, relationship to study product, time between onset and last vaccination, and number of vaccinations received.

#### 6.4.3.3 Local laboratory values

Boxplots of local laboratory values will be generated for baseline values and for values measured during the course of the study by treatment arm and visit. Each boxplot will show the first quartile, the median, and the third quartile. Outliers (values outside the boxplot) will also be plotted. If appropriate, horizontal lines representing boundaries for abnormal values will be plotted.

For each local laboratory measure, summary statistics will be presented by treatment arm and time point, as well as changes from baseline for post-enrollment values. In addition, the number (percentage) of participants with local laboratory values recorded as meeting Grade 1 AE criteria or above as specified in the DAIDS AE Grading Table (see Section 9.10) will be tabulated by treatment arm for each post-vaccination time point. Reportable clinical laboratory abnormalities without an associated clinical diagnosis will also be included in the tabulation of AEs described above.

#### 6.4.3.4 Reasons for vaccination discontinuation and early study termination

The number and percentage of participants who discontinue vaccination and who terminate the study early will be tabulated by reason and treatment arm.

### 6.4.4 Immunogenicity analysis

#### 6.4.4.1 General approach

For the statistical analysis of immunogenicity endpoints, data from enrolled participants will be used according to the initial randomization assignment regardless of how many injections they received. Additional analyses may be performed, limited to participants who received all scheduled injections per protocol. Assay results that are unreliable, from specimens collected outside of the visit window, or from HIV-infected participants postinfection are excluded. Since the exact date of HIV infection is unknown, any assay data from blood draws 4 weeks prior to an infected participant's last seronegative sample and thereafter may be excluded. If an HIV-infected participant does not have a seronegative sample postenrollment, then all data from that participant may be excluded from the analysis.

Discrete categorical assay endpoints (eg, response rates) will be analyzed by tabulating the frequency of positive response for each assay by antigen and treatment arm at each timepoint for which an assessment is performed. Crude response rates will be presented with their corresponding 95% CI estimates calculated using the score test method [70]. Fisher's exact tests will be used for the primary analysis comparing the IgG response rates of the arm with ALVAC primes followed by ALVAC + Bivalent Subtype C gp120 adjuvanted with MF59® boosts (Group 1) vs the aluminum hydroxide adjuvanted arm (Group 2) at Month 6.5 with a significant difference declared if the 2-sided p-value is  $\leq 0.05$ . Fisher's exact tests will also be used to compare IgA response rates between the arm with ALVAC primes and Bivalent Subtype C gp120 adjuvanted with MF59® boosts (Group 1) and the arm with ALVAC + Bivalent Subtype C gp120 adjuvanted with MF59® coadministered at all vaccination timepoints (Group 3) at Month 6.5; this is considered a separate primary objective and thus no multiplicity adjustment will be made. Fisher's exact tests will also be used to compare response rates between the unadjuvanted and adjuvanted arms at Month 6.5 and other time points; these analyses are viewed as secondary and therefore no multiplicity adjustment will be made.

For quantitative assay data (eg, level of vaccine-induced IgG Ab binding to the 2 gp120 Env proteins contained in the vaccine regimen), graphical and tabular summaries of the distributions by antigen, treatment arm, and timepoint will be made. The difference between arms at a specific timepoint will be tested with a nonparametric Wilcoxon rank sum test if the data are not normally distributed and with a 2-sample t-test if the data appear to be normally distributed. To test for differences among the 4 vaccine arms, first a Kruskal-Wallis rank test or an F-test (depending on the normality assumption) will be used to test for overall differences. Secondly, if the overall test is significant at the 2-sided 0.05 level, then individual tests comparing the 3 pairs of vaccine arms will be done unless pre-specified. If rank-based tests are used then the tests will be inverted to construct Hodges-Lehmann point-estimates and 2-sided  $(1 - 0.05/3) \times 100\%$  CIs about the differences in location centers of the 3 pair-wise comparisons of vaccine arms. An appropriate data transformation (eg,  $\log_{10}$  transformation) may be applied to better satisfy assumptions of symmetry and homoscedasticity (constant variance).

Some immunologic assays have underlying continuous or count-type readout that are dichotomized into responder/nonresponder categories (eg, binding antibody multiplex assay [BAMA]). If treatment arm differences for these assays are best summarized by a mixture model, then Lachenbruch's test statistic [71] will be used to evaluate the composite null hypothesis of equal response rates in the MF59® vs aluminum hydroxide adjuvanted arms and equal response distributions among responders in the 2 arms. This test statistic equals the square of a binomial Z-statistic for comparing the response rates plus the square of a Wilcoxon statistic for comparing the response distributions in the subgroup of responders. A permutation procedure is used to obtain a 2-sided p-value. For estimation, differences in response rates between arms will be estimated using the methods described above, and in the subgroup of positive responders, differences in location parameters between arms will be estimated using the methods described above.

This approach will also be used to compare the arm with ALVAC primes followed by ALVAC + Bivalent Subtype C gp120 adjuvanted with MF59® boosts at Month 3, 6, 12 (Group 1) to the arm with ALVAC + Bivalent Subtype C gp120 adjuvanted with MF59® coadministered at all vaccination timepoints (Group 3).

Based upon previous AIDS Vaccine Evaluation Group (AVEG) and HVTN trials, missing 15% of immunogenicity results for a specific assay is common due to study

participants terminating from the study early, problems in shipping specimens, or low cell viability of processed PBMCs. To achieve unbiased statistical estimation and inferences with nonparametric tests and generalized linear models fit by generalized estimating equation (GEE) methods, missing data need to be missing completely at random (MCAR). MCAR assumes that the probability of an observation being missing does not depend upon the observed responses or upon any unobserved covariates but may depend upon covariates included in the model (eg, missing more among whites than nonwhites). When missing data are minimal (specifically if no more than 20% of participants are missing any values), then nonparametric tests and GEE methods will be used, because violations of the MCAR assumption will have little impact on the estimates and hypothesis tests. These models will include as covariates all available baseline predictors of the missing outcomes.

If a substantial amount of immunogenicity data are missing (at least 1 value missing from more than 20% of participants), then using the methods that require the MCAR assumption may give misleading results. In this situation, analyses of the immunogenicity endpoints at a specific timepoint will be performed using parametric generalized linear models fit by maximum likelihood. These methods provide unbiased estimation and inferences under the parametric modeling assumptions and the assumption that the missing data are missing at random (MAR). MAR assumes that the probability of an observation being missing may depend upon the observed responses and upon observed covariates, but not upon any unobserved factors. Generalized linear models for response rates will use a binomial error distribution and for quantitative endpoints, a normal error distribution. For assessing repeated immunogenicity measurement, linear mixed effects models will be used. If the immunological outcomes are left- and/or right- censored, then the linear mixed effects models of Hughes [72] will be used, because they accommodate the censoring. In addition, secondary analyses of repeated immunogenicity measurements may be done using weighted GEE [73] methods, which are valid under MAR. All of the models described above will include as covariates all available baseline predictors of the missing outcomes.

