### 6.1.2 Sample size calculations for immunogenicity

The primary immunogenicity objective of this trial is to characterize the vaccine-induced humoral immune responses of the 4 vaccine regimens at Month 6.5. The precision with which the true response rate can be estimated from the observed data depends on the true underlying response rate and the sample size. Two-sided 95% CIs for the response rate based on observing a particular rate of responses in the vaccinees is shown in Table 6-3.

Calculations are done using the score test method [70]. The sample size  $n = 20$  and  $n = 30$  assume a 15% missing data rate.

Another primary question of interest regarding immunogenicity is the comparison of the Month 6.5 response rates of insert-directed serum IgG from the binding Ab assay to detect moderate differences in response rates between the 2 arms primed with ALVAC followed by ALVAC + Bivalent Subtype C gp120 adjuvanted either with MF59® or with alum. A separate primary objective is to compare the Month 6.5 response rates of insert-directed serum IgA from the binding Ab assay for the arm primed with ALVAC followed by ALVAC + Bivalent Subtype C gp120 adjuvanted with MF59® to the arm with concurrent administration of ALVAC and Bivalent Subtype C gp120 adjuvanted with MF59® at all vaccination timepoints. Within each of these group comparisons, no adjustment will be made for the use of multiple inserts.

**Table 6-3 Two-sided 95% CIs for the true response rate based on observing a particular rate of responses in the vaccinees ( $n = 20, 30$ )**

n	No. of responses	Observed response rate (%)	CI (%)
20	6	30.0	(14.5, 51.9)
20	10	50.0	(29.9, 70.1)
20	12	60.0	(38.7, 78.1)
20	14	70.0	(48.1, 85.5)
20	16	80.0	(58.4, 91.9)
30	9	30.0	(16.7, 47.9)
30	15	50.0	(33.2, 66.8)
30	18	60.0	(42.3, 75.4)
30	21	70.0	(52.1, 83.3)
30	24	80.0	(62.7, 90.5)

As shown in Table 6-4, there is adequate power for a formal comparison of immunogenicity response rates between adjuvanted vaccine arms of size  $n = 30$  to detect moderate differences in response rates of ~35%. These calculations use a Fisher's exact 2-sided test with a Type I error rate of 0.05.

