**Table 6-4 Power for comparison of response rates between 2 arms ( $n_1 = 30, n_2 = 30$ )**

True response rate Arm 1 (%)	Maximum true response rate in Arm 2 in order to detect a difference	
	80% power	90% power
40	8	5
50	14	10
60	22	18
70	32	27
80	42	37
90	56	51
95	64	59

In addition to comparing insert-directed serum IgG response rates at Month 6.5 between the aluminum hydroxide and MF59® adjuvanted arms, it is also of interest to compare

differences in the magnitudes of the responses. Power calculations use Lachenbruch's 2-part test to compare the response rates and the continuous insert-directed IgG responses at Month 6.5. Given that power is sufficient to compare the response rates, the study will also be well powered for this comparison involving magnitudes. For example, with  $n = 30$  per arm there is 80% power to detect a difference with a true response rate of 92% in 1 arm with  $GM = 6.31$  and variance of 2.06 in responders and a response rate of 80% in the other arm with  $GM = 5.18$  and variance of 2.06 in responders. Response rates of 92% and 94% with  $GMs$  of 6.31 and 6.42 (variance 2.06, 1.89 respectively) correspond to the responses observed at Month 6.5 in RV144 with the A244 and 92TH023 inserts. See Table 6-5 for power with other response rates and magnitudes (variance = 2.06 for each arm for true response rate = 92% and variance = 1.89 for true response rate = 94%)

Many other immunogenicity endpoints will also be analyzed to characterize the innate and adaptive immune profiles of the vaccine arms. These include vaccine-induced IgG Ab binding to V2 Env proteins, vaccine-induced CD4+ T-cell responses to the HIV proteins included in the vaccine and vaccine-induced IgG3 Ab binding to Env proteins.

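### Fisher's exact test for the two primary Month 6.5 response-rate comparisons is valid but conservative; Boschloo's exact test keeps the same 0.05 limit and never has less power

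*Combined protocol and SAP*

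**What the plan says.** Section 6.4.4.1 fixes the test for both primary response-rate contrasts at Month 6.5. For IgG, Group 1 (MF59) v Group 2 (alum): "Fisher's exact tests will be used for the primary analysis comparing the IgG response rates", "with a significant difference declared if the 2-sided p-value is" at most 0.05. For IgA, Group 1 v Group 3 (co-administration from Month 0): "Fisher's exact tests will also be used to compare IgA response rates", and "this is considered a separate primary objective and thus no multiplicity adjustment will be made". The same paragraph uses Fisher's test for the secondary contrasts with the unadjuvanted arm, Group 4.

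Section 6.1.2 powers the comparison with the same test: "These calculations use a Fisher's exact 2-sided test with a Type I error rate of 0.05". The planning sizes of 20 and 30 "assume a 15% missing data rate"; 36 enrolled x 0.85 = 30.6, and 24 x 0.85 = 20.4. The section concludes that "there is adequate power for a formal comparison of immunogenicity response rates between adjuvanted vaccine arms of size" 30, for differences of about 35 percentage points. Neither section gives a reason for a conditional test or mentions its actual size.

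**The concern.** Fisher's test conditions on the total number of responders. With about 30 per arm that leaves few attainable p-values, so the real type I error sits below the nominal level. In a small trial of fixed size, unused alpha is unused power. An exact unconditional test that orders tables by the Fisher p-value (Boschloo's) can spend that alpha without exceeding 0.05. At stake is some power in the two primary rate contrasts. Control of false positives is not in question.

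**Working it through.** **Inputs.** 30 v 30 evaluable, 2-sided 0.05, and the response-rate pairs of Table 6-4 (all from 6.1.2). IgG reference rates: 100% at Month 6.5 with the Group 1 regimen in HVTN 100 (4.11.1), and 92% and 94% in RV144 (6.1.2), whose protein boost was given with alum (4.1.1). The 80% and 85% comparator rates, 50% v 20-25%, and the unequal arm sizes are my assumptions, chosen to show the range.

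**Method.** Enumerate all 31 x 31 = 961 outcomes of two independent binomials. The Fisher 2-sided p-value sums the hypergeometric probabilities no larger than the observed one; reject if p <= 0.05. Size is the rejection probability at a common rate p, maximised over p. Boschloo's test rejects when the Fisher p-value is at or below the largest cut-off that keeps this maximum within 0.05. At 30 v 30 that cut-off is 0.0692.

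**Reproducing Table 6-4.** The column headed "Maximum true response rate in Arm 2 in order to detect a difference" reproduces with Fisher: 78.7-81.3% power at the 80% entries and 89.2-91.4% at the 90% entries.

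**Size at 30 v 30.** Fisher: maximum 2.74% (at p = 0.50), 2.2% at 0.80, 0.94% at 0.90, 0.59% at 0.92. Boschloo: maximum 4.69%. Boschloo rejects in 578 of the 961 outcomes and Fisher in 546, all of them among the 578, so Boschloo's power cannot be lower.

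**Power at 30 v 30 (%).**

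| True rates | Fisher | Boschloo | Gain |
|---|---|---|---|
| 40 v 8 | 78.7 | 82.1 | 3.4 |
| 50 v 14 | 80.9 | 84.7 | 3.8 |
| 60 v 22 | 80.3 | 86.2 | 5.9 |
| 70 v 32 | 79.3 | 84.7 | 5.4 |
| 80 v 42 | 81.0 | 86.7 | 5.7 |
| 90 v 56 | 80.8 | 83.7 | 2.9 |
| 95 v 64 | 81.3 | 85.4 | 4.1 |
| 50 v 20 | 59.6 | 67.1 | 7.5 |
| 50 v 25 | 41.3 | 50.2 | 8.9 |
| 100 v 85 | 28.9 | 47.6 | 18.7 |
| 100 v 80 | 57.2 | 74.5 | 17.3 |

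The gain near 100% comes from one boundary outcome. For 30/30 v 25/30, Fisher's p = 2 x C(30,5)/C(60,5) = 2 x 142,506/5,461,512 = 0.052, which is not significant; Boschloo's p = 0.027. With one arm at 100%, Fisher needs 24 or fewer responders in the other arm and Boschloo 25 or fewer.

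**Other arm sizes.**

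| Evaluable | Fisher maximum size | Fisher size at 90% response |
|---|---|---|
| 30 v 30 | 2.7% | 0.9% |
| 36 v 36 | 2.8% | 1.4% |
| 30 v 31 | 4.0% | 1.7% |
| 29 v 31 | 3.9% | 2.8% |
| 28 v 32 | 3.7% | 2.6% |
| 30 v 20 | 4.3% | 1.8% |

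- 36 v 36: the gain is 4-5 points at the same Table 6-4 pairs.
- 30 v 31, 29 v 31, 28 v 32: the gain at mid-range pairs runs from under 1 point (70 v 32) to about 6 points (50 v 20 at 29 v 31). At 100% v 80-85% it is 16-19 points when the smaller arm is the one at 100%. When the larger arm is at 100%, it is 13-20 points at 31 v 30 but nil at 31 v 29 and 32 v 28, because Fisher already rejects the boundary outcome there.
- 30 v 20 (Group 4 contrasts): about 0.5-2.3 points at 60 v 22, 80 v 42, 50 v 25 and 50 v 20; close to zero at 70 v 32; up to 5 points at 90 v 56. It is large only near 100% (100 v 80: 59% to 79%).

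**IgG at the documents' own rates (30 v 30).** 100 v 92: 2.9% (Fisher), 8.7% (Boschloo). 100 v 94: 0.8%, 3.2%.

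**The case against.** The strongest reply is that nothing here is wrong. Fisher's test controls type I error at 0.05, a stated rate of 0.05 is the usual nominal wording, and Table 6-4 was computed with the test that will be used, so the power claim is honest. That stands in full.

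A reader might infer from the 30 v 30 figures that the trial's real type I error will be at most 2.7%. The documents do not support this. Thirty per arm is a planning figure, evaluable numbers will often differ between arms, and one participant's difference raises the maximum to 4.0%.

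A reader might also infer that Boschloo's test would rescue the IgG contrast, since HVTN 100 places the MF59 regimen at 100%. No 80% or 85% alum estimate appears in the documents. At the 92-94% they do give, both tests are close to powerless.

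Nor do the primary objectives rest on Fisher alone. The endpoint covers occurrence and level, and 6.4.4.1 provides Wilcoxon or t-tests on levels, and Lachenbruch's two-part test where a mixture model fits best, for both primary contrasts.

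Last, the change is not entirely free. With three antigens per contrast and no adjustment across them, the Bonferroni bound on any false positive at 30 v 30 rises from 3 x 2.7% = 8% to 3 x 4.7% = 14%. That is still inside the 3 x 5% = 15% the plan already accepts.

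**Conclusion.** The point holds as a modest efficiency improvement. At exactly 30 v 30, Fisher's test gives up about 3-6 points of power at the 80% entries of Table 6-4, 7-9 points at 50% v 20-25%, and 17-19 points at 100% v 80-85%. With slightly unequal arms, most mid-range gains fall to a few points; near 100% they stay large in most layouts but depend on which arm is the smaller. Boschloo's power was never below Fisher's in any layout. The practical benefit lies mainly in the IgA contrast, for which the documents state no ceiling, and in an IgG contrast only if one arm falls clearly below the other. For Group 4 the case is weak away from 100%. The figures assume independent binomial responses and one test per antigen at 0.05.

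**What to change.** Before any unblinded Month 6.5 analysis (6.4.5.2 allows one once all participants have completed that visit and at least 80% have data), amend 6.4.4.1 to name Boschloo's 2-sided exact unconditional test at 0.05 for the response-rate comparisons. Name that one test only. Leaving a choice between Boschloo's and Barnard's tests would leave the rejection region open, because they differ. Define the statistic (the 2-sided Fisher p-value) and state that the p-value is maximised over the whole range of the common rate. Recompute Table 6-4 to match.

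The cost is protocol wording and one table, with no change to participants, visits or samples. Two downsides should be written down: the test is less familiar, and the realised false-positive rate per antigen moves closer to 0.05 with no adjustment across the three antigens. Naming a two-sample interval for the difference in rates would also help, since 6.4.4.1 specifies score intervals only for single-arm rates, but that is a separate reporting detail and this point does not depend on it.

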## 5 Objectives and endpoints

### 5.1 Primary objectives and endpoints

*Primary objective 1:*

To compare the humoral immune responses induced by ALVAC-HIV (vCP2438) prime with 2 ALVAC-HIV (vCP2438) + Bivalent Subtype C gp120/MF59® boosts or 2 ALVAC-HIV (vCP2438) + Bivalent Subtype C gp120 admixed with Aluminum Hydroxide Suspension boosts in HIV-uninfected participants

*Primary endpoint 1:*

Occurrence and level of vaccine-induced systemic IgG Ab binding to the 3 gp120 Env proteins contained in the vaccine regimen (ZM96, TV1.C, and 1086.C) at the Month 6.5 timepoint

*Primary objective 2:*

To compare the humoral immune responses induced by ALVAC-HIV (vCP2438) prime with 2 ALVAC-HIV (vCP2438) + Bivalent Subtype C gp120/MF59® boosts to the regimen with 3 ALVAC-HIV (vCP2438) + Bivalent Subtype C /MF59® vaccinations in HIV-uninfected participants

*Primary endpoint 2:*

Occurrence and level of vaccine-induced serum IgA Ab binding to the 3 gp120 Env proteins contained in the vaccine regimen (ZM96, TV1.C, and 1086.C) at the Month 6.5 timepoint

*Primary objective 3:*

To evaluate the safety and tolerability of each vaccine regimen through the Month 6.5 timepoint

*Primary endpoint 3:*

Severe local and systemic reactogenicity signs and symptoms (pain, tenderness, erythema, induration, fever, malaise/fatigue, myalgia, headache, nausea, vomiting, chills, arthralgia) within 3 days after each vaccine dose

AEs by body system, Medical Dictionary for Regulatory Activities (MedDRA) preferred term, severity, and assessed relationship to study products within 30 days after each vaccine dose

SAEs, AEs of special interest (AESIs), and new chronic conditions requiring medical intervention for  $\geq$  30 days, throughout the study

Laboratory measures: white blood cells (WBC), neutrophils, lymphocytes, hemoglobin, platelets, alanine aminotransferase (ALT), aspartate aminotransferase (AST), alkaline phosphate (ALP), and creatinine at baseline and following vaccinations

AEs leading to early participant withdrawal or early discontinuation of study product(s) administration throughout the study

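### IgG level is part of primary endpoint 1, but the only MF59 versus alum test labelled primary is Fisher's test on response rates, which loses almost all power if both arms respond near 100%

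*Combined protocol and SAP*

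**What the plan says.** Section 5.1 defines primary endpoint 1, at Month 6.5, as "Occurrence and level of vaccine-induced systemic IgG Ab binding to the 3 gp120 Env proteins contained in the vaccine regimen". Level is therefore primary by definition.

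Section 6.4.4.1 (General approach) takes rates first. For Group 1 versus Group 2, Fisher's "exact tests will be used for the primary analysis comparing the IgG response rates of the arm with ALVAC primes", and a difference is declared at a 2-sided p-value of 0.05 or less. No other test of this contrast is called primary or given a decision rule of its own.

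The same section then covers level in three ways:

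- A two-group comparison "will be tested with a nonparametric Wilcoxon rank sum test if the data are not normally distributed", and with a t-test if they look normal.
- A four-arm overall test at 0.05; if it is significant, "then individual tests comparing the 3 pairs of vaccine arms will be done unless pre-specified". Rank-based "tests will be inverted to construct Hodges-Lehmann point-estimates and 2-sided" intervals at the (1 - 0.05/3) level follow.
- The two-part test of MF59 versus alum with a permutation p-value, introduced by "If treatment arm differences for these assays are best summarized by a mixture model". For Group 1 versus Group 3, "This approach will also be used to compare the arm with ALVAC primes followed by" the protein-boost schedule.

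Section 6.1.2 calls the rate comparison a primary question and treats magnitude as an additional interest. It nevertheless bases power for the combined comparison on the two-part test, with no condition attached, and infers from adequate power for rates that the comparison involving magnitudes is well powered too.

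**The concern.** Section 4.9 states the expected adjuvant effect as one of magnitude: MF59 above alum. The only test labelled primary does not use magnitude. Section 4.11.1 reports that 100% of HVTN 100 vaccinees had binding antibody to all three vaccine gp120s at Month 6.5, and Section 4.8.2 says that this trial shares the schedule of the primary HVTN 100 regimen, which is the Group 1 regimen. If alum also brings nearly everyone above the positivity threshold, Fisher's test has little left to detect, and Objective 1 rests on level.

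For level, the plan does not say which result carries the conclusion. The condition for the two-part test has no criterion, and it concerns differences between arms, so it can be judged only from data by arm. Nor is it stated that Group 1 versus Group 2 is one of the pre-specified pairs exempt from the four-arm test. The text also speaks of three pairs, whereas four arms form six.

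**Working it through.** **Inputs.** 36 enrolled per adjuvanted arm and 15% missing (36 × 0.85 = 30.6), so the plan uses n = 30 per arm; Fisher's exact test, 2-sided 0.05 (Section 6.1.2). Group 1 response of 100% (Section 4.11.1). Group 2's rate is not given anywhere for these antigens, so it is varied. Two-part planning values: 92% and GM 6.31 versus 80% and GM 5.18, variance 2.06 (Section 6.1.2).

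**Reproducing the plan.** Exact enumeration of all outcomes reproduces Table 6-4: its 14 cells give 78.7% to 81.3% against a nominal 80%, and 89.2% to 91.4% against 90%. The two-part example, printed as 80%, gives about 77% by simulation with a permutation p-value. The other 80% entries of Table 6-5 give 75% to 82%, so that table reproduces approximately.

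**Fisher's test at the ceiling.** If all 30 in Group 1 respond, p = 0.0237 against 24/30 and p = 0.0522 against 25/30. The test rejects only when Group 2 has 24 or fewer responders, so power = P(X ≤ 24) with X ~ Binomial(30, p2):

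| Alum response rate | Fisher's power |
|---|---|
| 100% | 0% |
| 94% | 0.8% |
| 92% | 2.9% |
| 90% | 7.3% |
| 85% | 29% |
| 80% | 57% |
| 75% | 80% |
| 65% | 98% |

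The last row is a 35-point gap, the size that Section 6.1.2 targets; it is well powered.

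**The plan's own two-part alternatives.** At 92% versus 80%, Fisher's power is 14%, against about 77% for the two-part test. At two other response-rate pairs in Table 6-5, Fisher's power is 7% (94% versus 85%) and 38% (94% versus 75%). Power for rates is therefore not sufficient at these alternatives, and the inference in Section 6.1.2 fails there. The two-part power comes mainly from level.

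**Level when everyone responds.** The binomial term is then zero and the two-part statistic is the squared Wilcoxon statistic. With GM 6.31 versus 5.18 and variance 2.06, power is about 83%, against 0% for Fisher's test. This takes the GMs and variance to be on the scale where responder values are normal. The difference is 6.31 - 5.18 = 1.13. On a natural-log scale that is exp(1.13) = 3.1-fold; on log10 it would be 10^1.13 = 13.5-fold. Section 6.1.2 does not name the scale.

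**Sensitivity to the SD.** From Table 4-8, with a common SD in both trials, SD = ln(upper/lower) / 3.92 / √(1/185 + 1/201): for 1086, 0.289/3.92/0.1019 = 0.72; for ZM96, 0.398/3.92/0.1019 = 1.00. For a 2-fold difference with both arms at 100%, simulated two-part power is 95% at SD 0.72, 73% at SD 1.00 and 44% at √2.06 = 1.44.

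**Type I error from choosing a test.** Under the null, the chance that at least one of Fisher, Wilcoxon, t and two-part gives p ≤ 0.05 is about 6% at a common response rate of 100%, 7% at 92% and 9% at 80%. The plan states no free choice among four tests, so these are upper illustrations.

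**The case against.** The primary-analysis wording sits in a paragraph on categorical endpoints, and the next paragraph gives the level of IgG binding as its example. This can be read as one endpoint with its two components handled in turn. Section 6.1.2 names the two-part test for this contrast without any condition, and Table 6-5 covers high response rates. Group 1 versus Group 2 is Objective 1, so its natural reading is as a pre-specified pair. The ceiling is documented for the MF59 regimen only, and this is a phase 1/2a trial meant to characterise responses.

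Much of this stands, and it rules out stronger readings:

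- A reader might infer that level is unplanned. It is not: it is planned and powered.
- A reader might infer that nobody could tell which p-value answers Objective 1, or that data-driven choice seriously inflates error. The documents do not support that. When all respond, the two-part and Wilcoxon tests coincide apart from permutation noise. In simulation, Wilcoxon and t agreed in about 96% of trials at the planning difference, and the error figures above are modest.
- A reader might infer that Fisher's test should be demoted. Section 6.1.2 makes response rate a primary question in its own right, so nothing requires this.

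What the objection leaves unanswered is that Section 6.4.4.1 makes the powered test conditional, sets no criterion, and gives the primary label and decision rule only to a test that can have almost no power.

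**Conclusion.** The point holds as a mismatch between the primary endpoint and the analysis labelled primary. The harm is possible loss of power for the labelled analysis, not false positives. Its size depends on the unknown alum rate: with Group 1 at 100% and 30 evaluable per arm, Fisher's power falls from 80% at an alum rate of 75% to 7% at 90% and to zero at 100%. If alum responds at about 65% or lower, the labelled test works well.

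Independently of HVTN 100, the power inference in Section 6.1.2 is wrong at the plan's own example: 14% for rates against about 77% for the two-part test. The level figures rest on normal responder values and on the stated SD and scale. The ceiling figures concern IgG only; the documents give no corresponding IgA rate for Objective 2.

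**What to change.** In Section 6.4.4.1:

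- Keep Fisher's test as the primary analysis of occurrence.
- Remove the mixture-model condition for this contrast. State that the permutation two-part test, 2-sided 0.05, for each of ZM96, TV1.C and 1086.C at Month 6.5, is the primary analysis of occurrence and level together for Group 1 versus Group 2.
- State that the comparison is pre-specified and not gated on the four-arm test.
- Report with it the difference in response rates and the difference in magnitude among responders, each with a 95% CI, to show which part drives the result and in which direction.
- Say the same for IgA, Group 1 versus Group 3, which has the same form of endpoint.
- Leave the existing missing-data switch ("If a substantial amount of immunogenicity data are missing (at least 1 value missing from more than 20% of participants") as it is.

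In Section 6.1.2, delete the clause that infers power for magnitudes from power for rates. State Fisher's power when one arm is at or near 100%. State the two-part power when all respond, naming the SD and log scale: about 83% for GM 6.31 versus 5.18 with variance 2.06.

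Make the change before the unblinded Month 6.5 analysis that Section 6.4.5.2 allows. It needs no further participants, samples or assays. The cost is two primary tests for Objective 1 where the plan labels one, which fits the no-adjustment policy in Section 6.4. The two-part test is also an omnibus test, so it must be read with its component estimates.
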